STUDY PROTOCOL

1. Date: 01.01.2023

2. Official Title:

THE EFFECT OF A NEWLY FORMULATED PREOPERATIVE ORAL CARBONHYDRATE SOLUTION ON GASTRIC EMPTYING, POSTOPERATIVE NAUSEA AND VOMITING AND STRESS RESPONSE

3. Method:

109 patients who underwent elective laparoscopic cholecystectomy, aged 18-65 years and ASA physical state 1-2 were included in the study. The patients were divided into 3 groups: Group A, who would not eat anything 6-8 hours before the operation, Group S, who drank 400 ml of water 2 hours before the operation, and Group K, which drank 400 ml preoperative oral carbohydrate solution (PreOKH) 2 hours before the operation. Before induction of anesthesia (T1), patients antral gastric cross-sectional area (GKA) and gastric volume (GV) were evaluated by gastric ultrasound. The preoperative anxiety level of the patients was determined by the State-Trait Anxiety Inventory (STA1) before the operation (T1), and the symptoms affecting the preoperative patient comfort parameters (thirst, hunger, dry mouth, fatigue) were measured 2 hours before the operation (T0) and before the induction (T1) evaluated with the visual analog scale (VAS). Postoperative nausea and vomiting (PONV) and postoperative pain levels were recorded. Blood glucose, insulin and cortisol levels of the patients were measured 2 hours before the operation (T0), before induction (T1) and postoperative 2nd hour (T3).

Descriptive statistics of qualitative variables in the study will be given as number and percentage, and descriptive statistics of quantitative variables will be given as mean, median, standard deviation, minimum and maximum. Pearson chi-square and Fisher's exact chi-square tests will be used to compare the distribution of the relevant variables between the groups. The conformity of quantitative variables to normal distribution will be examined by Shapiro Wilk test. For normally distributed variables, one-way analysis of variance will be used to compare the means of more than two groups. Tukey test will be used as a posthoc test for pairwise comparisons. For non-normally distributed variables, Kruskall Wallis test will be used in the mean comparison of more than two groups and pairwise comparisons will be examined with Dunn test. Paired t test will be used for the mean comparison of two dependent groups and Wilcoxon signed-rank test will be used for median comparisons. Repeated measures analysis of variance method will be used for mean comparisons of more than two dependent groups and Friedman test will be used for median comparisons. Statistical significance level will be taken as 0.05 and SPSS (Version 28) package program will be used for calculations. For the gastric volume value, at the 95% confidence level, when the significance of a mean difference of 18.18 with 80% power is attributed (means 67.22 and 49.04 with standard deviations 29.49 and 15.4), a minimum of 28 people should be included in the study in each group. [1] Therefore, we planned the number of patients in the study groups as 30 for each group. 1

Inclusion Criteria:

1. Between the ages of 18-65
2. Elective laparoscopic cholecystectomy planned under general anesthesia
3. American Society of Anesthesiologists (ASA) class I-II physical condition

[figure not shown]
Exclusion Criteria:

1. Patients with gastroesophageal reflux and gastrointestinal motility disorders
2. diabetes mellitus
3. Mental retardation, previous neurological disease symptoms (syncope, dementia, alzheimer etc.)
4. Chronic alcoholism
5. Difficult Intubation
6. Patients with ASA physical status classes \geq III
7. Patients with a body mass index of 35 and above
8. History of meniere and motion sickness
9. Presence of previous history of postoperative nausea and vomiting
10. Smoking

Numerik Rank Score:

0: no vomiting or nausea
1: nausea
2: nausea and once vomiting
3: twice or more vomiting

VAS:

Qualitative evaluation of the antrum with gastric USG:

Grade 0: empty antrum both in the semi-sitting position and in the RLDP

Grade 1: gastric fluid is only visible in RLDP;

Grade 2: gastric fluid can be seen both in the semi-sitting position and in RLDP

Factor Loading

Item	I	II	h^2
1. I feel calm	.50	-.21	.41
2. I feel secure	.61	-.10	.45
3. I am tense	.01	.63	.39
4. I am strained	.05	.59	.32
5. I feel at ease	.59	-.05	.38
6. I feel upset	.03	.78	.58
7. I am presently worrying	-.01	.57	.33
8. I feel satisfied	.57	-.10	.39
9. I feel frightened	-.03	.69	.50
10. I feel comfortable	.59	-.19	.51
11. I feel self-confident	.70	.04	.46
12. I feel nervous	.05	.76	.54
13. I feel jittery	.01	.73	.52
14. I feel indecisive	-.09	.55	.37
15. I am relaxed	.58	-.10	.41
16. I feel content	.62	.06	.35
17. I am worried	.12	.79	.54
18. I feel confused	-.10	.62	.45
19. I feel steady	.69	-.01	.47
20. I feel pleasant	.68	.05	.43
21. I feel pleasant	.64	.02	.40
22. I tire nervous and restless	-.32	.44	.44
23. I feel satisfied with myself	.79	.09	.56
24. I wish I could be as happy as others seem	-.20	.23	.14
25. I feel like a failure	-.48	.15	.32
26. I feel rested	.61	.09	.33
27. I am calm, cool, and collected	.67	.03	.43
28. I feel that difficulties are piling...	-.34	.38	.39
29. I worry too much over something...	-.06	.37	.16
30. I am happy	.70	-.05	.52
31. I am inclined to take things hard	-.20	.38	.27
32. I lack self-confidence	-.38	.17	.25
33. I have disturbing thoughts	.78	.03	.59
34. I make decisions easily	.50	.02	.27
35. I feel inadequate	-.38	.21	.27
36. I am content	.70	-.07	.55
37. Some unimportant thought runs...	-.10	.34	.16
38. I take disappointments so keenly...	-.26	.28	.22
39. I am a steady person	.52	-.08	.32
40. I get in a state of tension or turmoil...	-.38	.30	.35

Note. Interfactor correlation = -0.52. Factor loadings are standardized regression coeff

FOLLOW-UP FORM

No:		Duration of operation	
Age-gender		Fasting time	
BMI		Anesthetic agent consumption	Sevoflurane: Remifentanil:
GRUP			
ASA		complications:	
disease		Antiemetic need :	

Gastric examination

Gastrik USG – measurement of CSA in RLPD (CSA = (LD × SD × π)/4)	LD:	SD:	CSA:
Gastric volume (GV = 27,0 + 14,6 × CSA (RLDP'de) – 1,28 × age)			
Qualitative evaluation score			
Gastiric volume (aspiration of ngs)			
Gastric pH			

Intraoperative vital sing

	HR	SP/DP	MAP	SpO ₂	BIS
Before induction					
İnd +1. min					
10. min					
20. min					
30. min					
40. min					
50. min					
60. min					
Before extubation					
After extubation					

PACU 1. min					
PACU 15.min					

	STAI	VAS	PONK	Glucose	Insulin	cortisole
Preop 2. hours						
Berofe induction						
PACU						
Postop 2. hours						
Postop 12. hours						
discharge						

Koordinatör: [name]. [name]

İmza

References

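### Does a count of 109 patients against a plan of 30 per group leave the analysed sample open to choice?

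*Combined protocol and SAP*

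**What the plan says.** Both figures come from section 3 (Method) of the combined protocol and SAP.

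- The opening paragraph gives the count: "109 patients who underwent elective laparoscopic cholecystectomy, aged 18-65 years and ASA physical state 1-2 were included in the study". It continues: "The patients were divided into 3 groups".
- The sample-size text works from gastric volume, "means 67.22 and 49.04 with standard deviations 29.49 and 15.4", and concludes that "a minimum of 28 people should be included in the study in each group". The next sentence sets the target: "Therefore, we planned the number of patients in the study groups as 30 for each group".
- The analysis text names the tests, for example "one-way analysis of variance will be used to compare the means of more than two groups", with Tukey comparisons to follow. It does not say which patients enter them.

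The document gives no dropout allowance, no group sizes for the 109, no replacement or withdrawal rule, no missing-data rule and no named analysis population.

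**The concern.** Three groups of 30 make 90, and the document reports 109. Nobody says whether the other 19 are over-recruitment, an allowance for losses, or patients later set aside. As the Method paragraph is worded, the 109 are the patients who were divided into groups, so the 19 seem to have been allocated.

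Two things would be at stake. If all 109 are analysed, the stated size and power are not those of the trial that was run. If the analysis is trimmed to about 30 per group, roughly one allocated patient in six is left out. With no rule in place, those omissions could be related to group and to gastric volume. That would be selection after allocation on the very outcome used to size the trial.

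**Working it through.** **Inputs** (section 3, Method): 109 included; 3 groups; 30 planned per group; minimum 28 per group; difference 18.18; SDs 29.49 and 15.4; power 80%; significance level 0.05. Sidedness is not stated. Two-sided is assumed because it reproduces the plan's figure and one-sided does not.

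**1. The plan's own figure.**
- Pooled SD = √((29.49² + 15.4²)/2) = √((869.66 + 237.16)/2) = 23.52.
- Standardised difference = 18.18/23.52 = 0.773.
- Two-sided t-test at 0.05 and 80% power: 27.28, rounded up to **28 per group**. The plan's figure is reproduced.
- The normal approximation gives 26.3, so 27. A one-sided t-test gives 21.4, so 22, which does not match.

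**2. The gap.**
- 3 × 30 = 90, and 109 − 90 = 19.
- 19/90 = 21.1% above plan; 19/109 = 17.4% of those included.
- 109/3 = 36.3, so the three groups cannot be exactly equal.
- Getting from 90 to 109 by a dropout allowance would need 90/(1 − 0.174) ≈ 109, a loss rate of about 17.4%. The document states no such rate.

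**3. Does either size fall short of the stated power?** Power for a difference of 18.18 at pooled SD 23.52, two-sided 0.05:

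| Per group | Unadjusted t-test | Tukey, three groups |
|---|---|---|
| 30 | 83.7% | 72.8% |
| 36 | 89.9% | 81.5% |

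The plan's power statement rests on the unadjusted two-group comparison, and on that basis both sizes exceed 80%. The lower Tukey figures come from sizing the trial on a single unadjusted pair. That is a separate matter, and there too the larger number helps.

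**4. How large could selection be?** Suppose 36 per group were cut to 30 by removing the six highest volumes (one sixth). For a normal variable the mean falls by φ(0.967)/(5/6) = 0.2499/0.8333 = 0.30 SD.
- One group only: 0.30 × 29.49 = 8.8 mL, or 0.30 × 15.4 = 4.6 mL. Against 18.18 mL these are 49% and 25%.
- Both compared groups trimmed the same way: 0.30 × (29.49 − 15.4) = 4.2 mL, or 23%.
- Removal unrelated to gastric volume: expected shift zero.

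The one-group case does not fit the scenario it is meant to illustrate. Keeping about 30 per group takes about six from every group.

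**5. The two statements side by side.** The opening paragraph is in the past tense and reports who was included. The sample-size sentence reports a plan, set above a stated minimum. They answer different questions, and a count above a minimum is consistent with it. No sentence provides for cutting the analysis to 30 per group.

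**The case for a change.** The strongest case for a change is that one document holds both figures, does not say which defines the analysed sample, and sets no rule for withdrawals. Gastric volume is measured before induction, after the fasting or drink assignment has taken effect. One listed exclusion, difficult intubation, may become known only at induction, when the outcome has already been recorded. Under the Tukey comparisons the plan names, moving from 30 to 36 per group takes power from below 80% to above it. A few sentences would settle all of this at no cost in patients or data.

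Part of this stands. The 19 are unexplained, an explicit analysis-set sentence would be good practice, and the document does not say how a late-recognised exclusion is handled.

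The rest does not carry a change. The missing analysis-set sentence would be missing at any sample size, so the 109 against 90 does not create that gap. Nothing documents 19 exclusions; the number is only a subtraction. Reasons such as a delayed operation or an unreadable or non-empty stomach are not among the exclusion criteria, and stomach content is itself an outcome recorded on the follow-up form. Unequal groups are no obstacle either: one-way analysis of variance, Tukey in its unequal-size form, Kruskal-Wallis and Dunn all accept them.

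**Conclusion.** No change to the plan follows. The difference of 19 is real and unexplained, but it lies between a target and a reported count, not between two rival sample sizes. Taken at its word, the plan puts the 109 divided patients into the named tests in their own groups, and that analysis is sound. Unadjusted power for 18.18 mL is 83.7% at 30 per group and 89.9% at 36, so the stated 80% is met at either size.

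The selection effect is hypothetical: zero in expectation if any losses are unrelated to volume, about 4.2 mL if both compared groups lost their top sixth, and 8.8 mL only if one group did and the other did not. The document gives no reason to expect any of the non-zero cases.

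This rests on three assumptions: a two-sided 0.05 level, the plan's own SDs, and an analyst who takes the ordinary default of analysing every allocated patient with a gastric measurement in the allocated group. The numbers allocated and analysed per group are facts for the final report's patient flow, which rewording the plan cannot supply.

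### The Method times anxiety at T1 only, names no subscale, and leads to an unadjusted comparison, forgoing the precision that a pre-drink State score (or the Trait score) would give

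*Combined protocol and SAP*

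**What the plan says.** **Timing.** Section 3 (Method) states: "The preoperative anxiety level of the patients was determined by the State-Trait Anxiety Inventory (STA1) before the operation (T1"). No other time is given for anxiety. The same sentence says of the comfort symptoms that they "were measured 2 hours before the operation (T0) and before the induction (T1) evaluated with the visual analog scale (VAS"), and the blood measures are timed at T0, T1 and T3.

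**Form.** The grid at the end of the follow-up form has a STAI column. Its rows run from two hours before the operation, through induction and recovery, to discharge. The form therefore has a place for a pre-drink STAI that the Method does not mention.

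**Score.** The Method names the inventory but no subscale, total or scoring rule. The item table headed Factor Loading lists 40 items without labelling a State half and a Trait half. Items 1-20 are worded mainly as present feelings. Many of items 21-40 describe a disposition, for example "39. I am a steady person".

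**Analysis.** The statistical paragraph of section 3 gives general rules by type of variable. A quantitative variable measured once in three groups goes to one-way ANOVA with Tukey, or Kruskal-Wallis with Dunn. Dependent measurements get paired or repeated-measures tests. No covariate is named for any outcome.

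**The concern.** Anxiety before surgery varies widely between people for reasons unrelated to a drink. A single post-drink score carries all of that variation into the error term. It also gives no means of checking whether the groups were equally anxious beforehand, or of correcting for it if they were not. With about 30 patients per group, chance differences of a size that matters are to be expected.

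The plan already has the means to do better: a form row at T0, and an inventory whose name covers a trait component. The statistical paragraph gives neither a role. If staff do complete the T0 row, the listed tests would use it only for change over time within patients, not to sharpen the between-group comparison.

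Leaving the score unnamed adds a second exposure. The analyst could choose State, Trait or a total after seeing the data, and a total would be less sensitive to a short-term effect.

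**Working it through.** **1. The plan's own figure.** The only calculated figure concerns gastric volume: "means 67.22 and 49.04 with standard deviations 29.49 and 15.4", from which "a minimum of 28 people should be included in the study in each group".
- Pooled SD = √((29.49² + 15.4²)/2) = √553.41 = 23.52.
- Standardised difference = 18.18/23.52 = 0.773.
- At two-sided 0.05 and 80% power, the normal approximation gives 27 per group. The t-based calculation gives 28 (power 79.6% at 27, 81.1% at 28).

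The stated 28 reproduces, but it says nothing about anxiety.

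**2. Inputs for anxiety.**
- From the documents: 30 per group planned, and significance level 0.05 (taken as two-sided).
- Assumed, because the documents give no value: a true State difference d = 0.5 SD, and a correlation r between the covariate (T0 State, or Trait) and T1 State of 0.5-0.7.
- Not used: "Interfactor correlation = -0.52". It relates factors I and II of the item analysis and is not stated to be a state-trait correlation.

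**3. Gain from adjustment.** Adjusting for a covariate multiplies the residual variance by 1 − r², so the effective standardised difference is d/√(1 − r²). Noncentral-t power for a single two-sided comparison at 30 per group:

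| Analysis of T1 State | Residual variance | Effective d | Power |
|---|---|---|---|
| Unadjusted | 1.00 | 0.500 | 48% |
| Adjusted, r = 0.3 | 0.91 | 0.524 | 51% |
| Adjusted, r = 0.5 | 0.75 | 0.577 | 59% |
| Adjusted, r = 0.7 | 0.51 | 0.700 | 76% |

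The Method also reports 109 patients, or 109/3 ≈ 36 per group. At 36 the figures are 55% unadjusted and 68-83% adjusted for r = 0.5-0.7. The ordering does not depend on which sample size is used.

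**4. Chance imbalance.** At 30 per group, the standard error of a between-group difference in a baseline score is √(2/30) = 0.258 SD. Its 95% range is ±1.96 × 0.258 = ±0.51 SD. An imbalance at that limit would shift the unadjusted T1 difference by r × 0.51, which is 0.25 SD at r = 0.5 and 0.35 SD at r = 0.7. The assumed drink effect is 0.5 SD.

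**5. Only if State and Trait were totalled.** Suppose the two parts have equal SDs and state-trait correlation ρ, and only State responds. The SD of the sum is then √(2 + 2ρ) times the State SD. The difference in points is unchanged, and the standardised effect is multiplied by 1/√(2 + 2ρ):

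| ρ | Factor | Fall | Power for d = 0.5, 30 per group |
|---|---|---|---|
| 0 | 0.71 | 29% | 27% |
| 0.5 | 0.58 | 42% | 20% |
| 0.7 | 0.54 | 46% | 18% |

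With a Trait SD of 0.6 to 1.2 times the State SD and ρ from 0 to 0.9, the factor runs from 0.86 to 0.47. If State is scored alone, the factor is 1.

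**The case against.** The strongest reply is that nothing here is an error. A T1-only comparison does not shrink or bias the between-group difference when allocation is random (the Method says only that patients were divided into groups). Adjustment is an efficiency gain. Anxiety is not in the trial's title, and the sample size rests on gastric volume. The power figures use assumed inputs and a single t-test, not the planned three-group test with Tukey or Dunn comparisons. All of that stands. It limits the weight of the point and does not remove it.

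A reader might go further and infer that the plan analyses one 40-item score, that no pre-drink value exists, and that a real effect would therefore be roughly halved. The documents do not support this:
- **Combined score.** No section says the items are summed. The single STAI cell per time on the form is weak evidence, because the same grid has one VAS cell per time although the Method uses VAS for four symptoms. The item table reports factor loadings and is not a scoring sheet. It does not show that all 40 items are administered.
- **No pre-drink value.** The Method names only T1, but the form has the T0 row. The grid is generic, so that row does not prove collection either. The two places need reconciling.
- **Halving.** For a summed score the raw difference is unchanged. With equal SDs the standardised effect falls by exactly half only at ρ = 1.

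**Conclusion.** The point holds as an efficiency and specification weakness in a supporting outcome. The Method and the form differ on whether anxiety is recorded before the drink, the score is not named, and the stated tests make no use of any baseline. On the assumptions above, adjustment cuts residual variance by 25-49% and raises illustrative power from 48% to about 59-76%. At r = 0.3 the gain is small, 48% to 51%. These figures show direction and rough size and are not the power of the planned three-group analysis.

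Dilution through a combined score is a conditional risk that a scoring sentence removes. It is not a defect the documents establish. Even with the adjustment, a null anxiety result at this sample size would be limited evidence of no effect.

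**What to change.** 1. Reconcile section 3 with the follow-up form: state that the State part of the inventory is completed at T0, before the drink, and again at T1.
2. Name the T1 State score as the anxiety outcome, and state which items form it and how it is scored. Give State and Trait separate cells on the form.
3. In the statistical paragraph, compare T1 State across the three groups by ANCOVA adjusted for T0 State, with adjusted pairwise comparisons. If T0 State is not collected, use the Trait score as the covariate. The Method is written partly in the past tense, so this fallback may be the only option for patients already measured.
4. If residuals are clearly non-normal, use a rank-based ANCOVA in place of an unadjusted Kruskal-Wallis test.

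The cost is a few minutes of patient time at T0, one extra cell on the form, a scoring sentence and one covariate. The Trait fallback adds patient time only if the Trait items are not already being asked, which the documents leave open.

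### Cortisol samples are timed only relative to surgery, and the form has no clock-time field, so time of day adds noise to group comparisons, could bias them unseen, and confounds within-group change

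*Combined protocol and SAP*

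**What the plan says.** Stress response is one of the three aims in the title, and cortisol is the stress hormone measured for it. The Method section sets the schedule: "Blood glucose, insulin and cortisol levels of the patients were measured 2 hours before the operation (T0"), then again before induction (T1) and at the second hour after surgery (T3). All three times are relative to the operation.

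The surgical inclusion criterion is "Elective laparoscopic cholecystectomy planned under general anesthesia". None of the three inclusion or ten exclusion criteria mentions time of day or list position. The Follow-up Form records operation duration and fasting time. Its hormone rows carry nominal labels such as "Postop 2. hours", with no field for the clock time of surgery or of a blood sample.

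On allocation, the Method section says only "The patients were divided into 3 groups". It states no randomisation, stratification or list-order rule.

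For normally distributed variables, the statistical paragraph says "one-way analysis of variance will be used to compare the means of more than two groups", with Kruskal-Wallis as the alternative and no covariate in either case. For measurements over time it says "Repeated measures analysis of variance method will be used for mean comparisons of more than two dependent groups", and it also lists paired t, Wilcoxon and Friedman tests.

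**The concern.** Cortisol has a daily rhythm and falls over the usual operating day. A patient first on the list and a patient operated on in the afternoon are therefore sampled at different points of that fall, although both samples carry the label T0. Three consequences need to be kept apart.

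- **Noise.** Start-time spread within groups widens the cortisol distribution at each time point and costs power.
- **Possible bias.** If one group is operated on later on average, its cortisol is lower at each time point for that reason alone. This could be read as a smaller stress response.
- **Within-group change.** A test of T0 against T3 in one group includes several hours of daily fall, which could create a change or mask one.

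The plan has no step that measures, balances or adjusts for clock time.

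**Working it through.** **The plan's own figure.** The only sample-size calculation is for gastric volume: difference 18.18, SDs 29.49 and 15.4. The pooled SD is √((29.49² + 15.4²)/2) = 23.52. A two-sided t-test at 0.05 has power 0.796 with 27 per group and 0.811 with 28, so the stated minimum of 28 reproduces. It does not bear on cortisol, for which the documents give no SD, effect size or slope.

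**Inputs.** From the documents: 30 planned per group and "Statistical significance level will be taken as 0.05" (taken as two-sided). Assumed: cortisol falls 0.6-1.2 µg/dL per hour at a constant rate; between-patient SD at a fixed clock time is 5 µg/dL; start-time SD is 2 h; surgery lasts 1 h.

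**1. Balanced start times, single time point.** With SD 5 and 30 per group, a pairwise t-test has 80% power for a difference of 3.68 µg/dL. Start-time spread gives a total SD of √(25 + (slope × 2)²):
- slope 0.6: √(25 + 1.44) = 5.14, power 77.8%;
- slope 1.2: √(25 + 5.76) = 5.55, power 71.4%.

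There is no bias. In a simulation with no true effect, falls of 0.1-0.3 SD per hour and start times spread evenly over 8 h in all groups, the ANOVA false-positive rate was 0.049-0.052.

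**2. Start times that differ systematically by group.** Bias in a raw T1 or T3 comparison = slope × gap.
- Gap 1 h: 0.6-1.2 µg/dL, or 16-33% of 3.68 (0.6/3.68, 1.2/3.68). The pairwise false-positive rate rises from 5% to about 7-13%.
- Gap 2 h: 1.2-2.4 µg/dL, or 33-65% of 3.68. The rate rises to about 14-38%.

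The chance variation in the gap has standard error 2 × √(2/30) = 0.52 h. A 2 h gap is 2/0.52, about 3.9 standard errors, so it would need scheduling that depends on group.

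**3. Between-group comparison of change.** Under a constant slope every patient loses the same amount from T0 to T3 whatever the start time. The comparison of change then has neither bias nor added noise from start time. Bias would remain only to the extent that the slope itself varies over the day, which these assumptions do not quantify.

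**4. Within-group change.** T0 to T3 spans about 2 + 1 + 2 = 5 h, so the daily fall alone is 5 × 0.6 = 3 to 5 × 1.2 = 6 µg/dL. For a paired t-test with 30 patients and an SD of change equal to one between-patient SD, falls of 0.1, 0.2 and 0.3 SD per hour give a significant change, with no surgical or treatment effect, in 75%, about 100% and about 100% of trials. The slopes assumed above are 0.12-0.24 SD per hour (0.6/5 and 1.2/5), within that range.

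**The case against.** The strongest reply is that the effect of fasting, water or the solution is a contrast between concurrent groups sampled at the same relative times, so a fall common to all groups cancels. That stands. A reader might infer from the missing clock times that the daily fall is already mixed into the group effect. The documents do not support that inference, because it requires start times to differ by group and nothing shows that they do.

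A reader might also infer that Groups S and K would be pushed later on the list because they need a supervised drink. The Method section schedules T0 blood and symptom scores for all patients, so Group A needs the same early visit. Only the drink differs, and no text links it to list position. That mechanism is conjecture.

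T0 cortisol is measured in every group and would show a large imbalance indirectly. This is true, but the check is weak. Under the assumptions above, a raw T0 comparison would reach significance only about 7-13% of the time for a 1 h gap and 14-38% for a 2 h gap.

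Finally, the within-group tests come from a generic list, and nowhere does the plan say that within-group cortisol change will be read as a treatment effect. That is also true, so the point asks for a limit on interpretation and does not allege a stated misuse. It remains that the plan gives no allocation method, which is the safeguard that would rule out systematic imbalance.

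**Conclusion.** The point holds in a limited form. The omissions are plain in the text: relative timing only, no time-of-day restriction, no clock-time field, no stated allocation method and no covariate. The consequences differ in certainty.

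- For single-time-point group comparisons with balanced start times, the cost is precision: 80% power becomes about 78-71%.
- If start times differ by group, raw T1 and T3 comparisons are biased by 0.6-1.2 µg/dL per hour of gap. The form could not directly check this. It is a possibility, not a finding.
- Within-group T0-T3 tests cannot separate the daily fall from the response to surgery or regimen, however well the groups are balanced.

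All cortisol magnitudes rest on the assumed slope, SD, start-time spread and surgery length. The gastric-volume endpoint that sets the sample size is unaffected.

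**What to change.** 1. Record the clock times of the T0, T1 and T3 samples on the Follow-up Form. The Method section is partly in the past tense, so enrolment may be over; in that case retrieve the times if source records hold them.
2. Report T0 clock time by group, and state how patients were allocated.
3. Replace the unadjusted cortisol ANOVA with a between-group comparison of T1 and T3 cortisol adjusted for T0 cortisol and clock time (analysis of covariance). Confirm that the T0 sample precedes the drink, since adjustment for T0 relies on this and the text does not give the order.
4. State that within-group cortisol change alone will not be interpreted as stress response or treatment effect.

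The cost is three recorded times per patient and one or two degrees of freedom. If the daily fall is roughly linear, the adjustment recovers most of the power lost to start-time spread. Restricting eligibility to a common morning slot is optional, may be moot if enrolment is complete, and is not needed for this fix.

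### The ordered antral grade is routed to chi-square/Fisher tests that ignore order, and the ordered PONV score is assigned to no test

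*Combined protocol and SAP*

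**What the plan says.** In the combined protocol and SAP, the statistical paragraph of section 3 (Method) has two branches for comparing groups.

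- **Qualitative variables** are summarised by number and percentage. The next sentence reads "Pearson chi-square and Fisher's exact chi-square tests will be used to compare the distribution of the relevant variables between the groups". The variables meant are not listed, and no pairwise follow-up is named.
- **Quantitative variables** are checked by Shapiro-Wilk. They then go to analysis of variance with Tukey, or to Kruskal-Wallis with Dunn.

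There is no third branch for ordered categories, and neither of the two ordered scores is assigned to a test by name.

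- **Antral grade.** The scale is headed "Qualitative evaluation of the antrum with gastric USG". It runs from an empty antrum (0), through fluid seen in one position only (1), to fluid seen in both (2). The follow-up form again calls it a qualitative score.
- **PONV score.** Under the heading Numerik Rank Score, it runs from no symptoms (0) and nausea alone (1), through "2: nausea and once vomiting", to repeated vomiting (3).

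The only sample-size calculation is for gastric volume. It leads to the statement that "we planned the number of patients in the study groups as 30 for each group".

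**The concern.** Both scales are graded: a higher number means more fluid or worse symptoms. Pearson chi-square and Fisher's exact test give the same result if the category labels are shuffled. They spread their power over every way in which the group distributions could differ, including ways that make no sense on a severity scale. A rank test concentrates on a shift up or down, which is what these scales are built to show.

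For the antral grade, the plan's wording leads to the less sensitive test. For PONV, which is in the trial's title, the choice is open. The analyst could settle it after seeing the data, between two tests of materially different power.

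The chi-square branch also names no pairwise procedure. In a three-group trial, a significant result on either score would leave no planned way of saying which group differs.

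**Working it through.** **1. The plan's own figure.** The inputs are "means 67.22 and 49.04 with standard deviations 29.49 and 15.4", 80% power, and "Statistical significance level will be taken as 0.05" (two-sided assumed).

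- Root mean square SD = √((29.49² + 15.4²)/2) = √553.41 = 23.52.
- Normal approximation: n = 2 × (1.960 + 0.842)² × 553.41 / 18.18² = 26.3, so 27 per group.
- The t-test version gives 79.6% power at 27 and 81.1% at 28.

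The stated 28 therefore reproduces. It concerns gastric volume and says nothing about power for the two ordered scores.

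**2. Degrees of freedom.** With three groups, Pearson chi-square has (3−1)(3−1) = 4 df for the antral grade and (3−1)(4−1) = 6 df for PONV. Kruskal-Wallis has 3−1 = 2 df for either. As a check, suppose that both tests carry the same noncentrality, as is roughly so under a consistent shift. Where the 2-df test has 80% power, chi-square has 69.8% on 4 df (loss 10.2 points) and 62.5% on 6 df (loss 17.5). For 2-df power between 50% and 90%, the loss is 7 to 12 points (antral) and 14 to 19 points (PONV).

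**3. Simulation.** Assumptions, none of them given in the documents: the control splits below, two groups alike, and one group with its cumulative odds multiplied or divided by the odds ratio (OR). Example: antral control 30/45/25% has cumulative odds 0.30/0.70 = 0.429 and 0.75/0.25 = 3. Multiplied by 3 these become 1.286 and 9, so the shifted group is 56.25/33.75/10%. The tests are Pearson X² = Σ(O−E)²/E and tie-corrected Kruskal-Wallis, both at 0.05, with three groups of 30 and 8,000 to 20,000 simulated trials per setting. Losses are taken before rounding.

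| Score | Control split (%) | Shift in one group | Chi-square | Kruskal-Wallis | Loss (points) |
|---|---|---|---|---|---|
| Antral | 30/45/25 | OR 3, emptier | 50% | 61% | 11 |
| Antral | 50/35/15 | OR 2, fuller | 22% | 29% | 7 |
| Antral | 50/35/15 | OR 3, fuller | 52% | 64% | 11 |
| Antral | 50/35/15 | OR 6, fuller | 94% | 97% | 3 |
| PONV | 60/20/10/10 | OR 3, milder | 27% | 46% | about 20 |
| PONV | 50/25/15/10 | OR 3, milder | 34% | 54% | 20 |
| PONV | 60/20/12/8 | OR 2, worse | 18% | 29% | 11 |
| PONV | 60/20/12/8 | OR 3, worse | 46% | 65% | 20 |
| PONV | 60/20/12/8 | OR 6, worse | 91% | 98% | 6 |

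Over the splits tried, both directions and OR 2 to 4, the loss is about 5 to 13 points for the antral grade and 7 to 24 for PONV. Type I error was at or below about 5% for both tests, so the gain is not bought with false positives.

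**4. Larger sample.** Section 3 gives 109 patients. Split 36/36/37 with OR 3, the loss is 11 to 12 points (antral) and 19 to 21 (PONV).

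**5. Sparse cells.** In the first PONV row, the top two categories each hold about 8% over the three groups, so the expected count is about 30 × 0.08 = 2.4 in each of 6 of the 12 cells. Fisher's exact test would deal with the sparseness but would still ignore the order. Its power was not simulated.

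**The case against.** **The plan does not send PONV to chi-square.** A reader might infer that both scores fall under that rule. The documents do not support this. The PONV heading speaks of a numeric rank score. Treated as quantitative, a 0 to 3 score would very probably fail Shapiro-Wilk and go to Kruskal-Wallis with Dunn, which is the method recommended here. For PONV the defect is a missing assignment, not a wrong test. This stands.

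**The loss is not a property of the plan.** A reader might want one figure for the power lost. None can be given, because it depends on category rates, an effect size and a pattern of difference that the documents do not state. This stands, and the figures above are conditional.

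**A rank test can do worse.** With 30 per group and assumed antral splits of 40/30/30% in two groups and 20/65/15% in the third, chi-square has 73% power and Kruskal-Wallis 7%. With PONV at 50/20/15/15% in two groups and 50/42/6/2% in the third, it is 52% against 12%. This is a genuine downside. It needs a non-monotone difference or one with offsetting moves, and not the general shift toward more or less fluid or vomiting that these scales grade.

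**Chi-square is valid.** It holds its error rate, so the point is one of efficiency and specification, not of bias. This stands.

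**The gastric-emptying aim does not hang on the antral grade.** Section 3 names antral cross-sectional area and gastric volume as the gastric outcomes, and only gastric volume is powered. The grade appears as a scale definition and one line of the follow-up form. A reader who took it to carry that title aim would be going beyond the documents.

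**Conclusion.** The point holds in a limited form. On the natural reading of the plan, the ordered antral grade is compared by tests that discard its order, and the ordered PONV score has no assigned test. The size rests on 30 per group, one group differing by a consistent proportional-odds shift, OR 2 to 4 and assumed control splits. On those terms chi-square gives up about 5 to 13 points of power to Kruskal-Wallis for the antral grade. It gives up about 7 to 24 for PONV, and only if PONV is sent to chi-square. Losses are similar with 109 patients and shrink for effects so large that both tests approach full power. Importance is low to moderate: the antral grade is a supporting measure, but PONV is a title outcome whose test should not be left open.

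**What to change.** Add to the statistical paragraph that the antral grade (0 to 2) and the PONV score (0 to 3) are ordinal. State that they will be compared across the three groups by Kruskal-Wallis with multiplicity-adjusted Dunn tests for pairs, or by a proportional-odds model. Keep chi-square and Fisher for unordered variables such as sex and the presence of complications, and list those variables by name. Counts and percentages per category should still be shown, so that a non-monotone pattern can be seen even if the rank test misses it.

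The cost is one or two sentences. Kruskal-Wallis and Dunn are already in the plan, and no new data, patients or software are needed. The price is lower power if the groups differ in a non-monotone way.
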